8.4.1 Time Period and Frequency for Collecting AE and SAE Information

(S)AEs will be collected from the start of study intervention until the last FU visit (28 days after EOT) at the time points specified in the SoA (Section 1.3). (S)AEs which are related to protocol-required study procedures (e.g., (S)AE related to invasive study procedures) will be recorded as (S)AEs from the signing of the ICF.

Any medical occurrences/conditions that begin in the period between signing ICF and the start of study intervention, and which are not related to a protocol-required study procedure, will be recorded as medical history/current medical conditions, not as AEs.

All SAEs will be recorded and reported to the sponsor or designee immediately and under no circumstance should this exceed 24 hours, as indicated in Section 10.3. The investigator will submit any updated SAE data to the sponsor within 24 hours of it being available.

Investigators are not obligated to actively seek AE or SAE after conclusion of the study participation. However, if the investigator learns of any SAE, including a death, at any time after a participant has been discharged from the study, and the investigator considers the event to be reasonably related to the study intervention or study participation, the investigator must promptly notify the sponsor.

8.4.2 Method of Detecting AEs and SAEs

The method of recording, evaluating, and assessing causality of AE and SAE and the procedures for completing and transmitting SAE reports are provided in Section 10.3.

Care will be taken not to introduce bias when detecting AEs and/or SAEs. Open-ended and non-leading verbal questioning of the participant is the preferred method to inquire about AE occurrences.

8.4.3 Follow-up of AEs and SAEs

After the initial AE/SAE report, the investigator is required to proactively follow each participant at subsequent visits/contacts. All SAEs and AESIs (as defined in Section 8.4.8), will be followed until resolution, stabilization, the event is otherwise explained, or the participant is lost to follow-up (as defined in Section 7.3). Further information on follow-up procedures is provided in Section 10.3.

8.4.4 Regulatory Reporting Requirements for SAEs

- Prompt notification by the investigator to the sponsor of an SAE is essential so that legal obligations and ethical responsibilities towards the safety of participants and the safety of a study intervention under clinical investigation are met.
- The sponsor has a legal responsibility to notify both the local regulatory authority and other regulatory agencies about the safety of a study intervention under clinical investigation. The sponsor will comply with country-specific regulatory requirements relating to safety reporting to the regulatory authority, Institutional Review Boards (IRB) / Independent Ethics Committees (IEC), and investigators.
- An investigator who receives an investigator safety report describing an SAE or other specific safety information (e.g., summary or listing of SAEs) from the sponsor will review and then file it along with the Investigator's Brochure and will notify the IRB/IEC, if appropriate according to local requirements.
- For all studies except those utilizing medical devices investigator safety reports must be prepared for suspected unexpected serious adverse reactions (SUSAR) according to local regulatory requirements and sponsor policy and forwarded to investigators as necessary.

8.4.5 Pregnancy

- Details of all pregnancies in female participants and in female partners of male participants will be collected after the start of study intervention and until last safety FU visit, but at least until 2 weeks after the last dose of study intervention in case of early termination.
- If a pregnancy is reported, the investigator will record pregnancy information on the appropriate form and submit it to the sponsor within 24 hours of learning of the pregnancy and should follow the procedures outlined in Section 10.4.
- While pregnancy itself is not considered to be an AE or SAE, any pregnancy complication or elective termination of a pregnancy for medical reasons will be reported as an AE or SAE.
- Abnormal pregnancy outcomes (e.g., spontaneous abortion, fetal death, stillbirth, congenital anomalies, ectopic pregnancy) are considered SAEs, and will be reported as such.
- The participant/pregnant female partner will be followed to determine the outcome of the pregnancy. The investigator will collect follow-up information on the participant / pregnant female partner and the neonate and the information will be forwarded to the sponsor.
- Any post-study pregnancy-related SAE considered reasonably related to the study intervention by the investigator will be reported to the sponsor as described in

Section 8.4.4. While the investigator is not obligated to actively seek this information in former study participants/pregnant female partner, the investigator may learn of an SAE through spontaneous reporting.

• Any female participant who becomes pregnant while participating in the study will discontinue study intervention.

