1.3 Schedule of activities (SoA)

		Scree	ning	Inter	venti	on per	riod		Follow-up
	(For footnotes, see next page.)			Randomization		•		EOT ¹	Days after last dose 28 ²
	Visit	1	2	3	4	5	6	7	8 (EOS)
	Day	-28 to-14	-8 +1	1	14 ±2	28 ±2	56 ±3	84 ±3	112 ±3
	General Informed Consent	•							
	Consent Skin Biopsy ³	•							
	Consent Photography ³	•							
	Demography	•							
5	Quantiferon TB Gold Plus test	•							
io	HIV, hepatitis B and C	•							
iat	SARS-CoV-2 RNA test ⁴		٠						
nit	Medical history / history of AD	•							
	Prior medication / prior AD therapy	•		•					
	Height	•							
	Weight	•		•	٠	•	•	٠	•
	Check of in-/exclusion criteria	•	٠	•					
	Randomization			•					
2	IRT registration	•		•	•	•	•	•	
atio	Study intervention dispensation			•	•	•	•		
i č	Study int. return / accountability				•	٠	•	٠	
ea	Study intervention intake			•→	or	ngoing		→	
S	Enter intervention intake into			·	or	ngoing		→	
	eDiary					 			
	Concomitant medication	•	٠	•	•	•	•	•	•
	ClinROs								
>		•		•	•	•	•	•	•
ac	- VIGA-AD	•		•	•	•	•	•	•
ЦС	- BSA affected by AD	•		•	•	•	•	•	•
Ш	 Dispense and training of patient handheld device 		•						
	- Daily Peak Pruritus 0-10 NRS ⁶		←		ong	going -			→
	- Return handheld device								•
	Other procedure: photograph ⁰			•				•	•
	Complete physical examination	•		•				•	٠
	Symptom-directed PE/inspection		•		•	•	•		
>	AE/SAE assessment	•8	• ⁸	•	٠	•	٠	٠	•
etj	AESI assessment	•8	• ⁸	•	٠	•	٠	٠	•
Safe	Pregnancy test – S(erum) / U(rine)	●s	●S	●U	●U	●U	●U	●U	●S
	Safety panel (central lab)9	•	● ¹⁰	•	•	•	•	•	•
	Lipid profile (central lab)			•				٠	
	Urinalysis	•	● ¹⁰	•		٠		٠	•
	12-lead ECG ¹¹	•			•			•	•
_	Vital signs	•	•	•	•	٠	•	•	•
ð	BM blood samples ¹²			•				•	
3	BM on-study skin biopsy ^{13,14}			•				•	
đ	PK blood sample			●15	● ¹⁶	●16	●16	●15,16	

Footnotes for schedule of activities (see next page)

Footnotes for schedule of activities

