AD = atopic dermatitis; AE(SI) = adverse event (of special interest); BM = biomarker; BSA = body surface area; ClinROs = clinician-reported outcomes; CRP = C-reactive protein; EASI = Eczema Area and Severity Index; ECG = electrocardiogram; eDiary = electronic diary (= patient handheld device); EOS = end of study; EOT = end of treatment; HIV = human immunodeficiency virus; IRT = Interactive Response Technology; NRS = numerical rating scale; PD = pharmacodynamc(s); PE = physical examination; PK = pharmacokinetic(s); PRO = patientreported outcome; RNA = ribonucleic acid; SAE = serious adverse event; SARS-CoV-2 = severe acute respiratory syndrome coronavirus 2; v = visit; vIGA-AD = validated Investigator's Global Assessment for Atopic Dermatitis

Early Discontinuation: Visit 7 (EOT) and Visit 8 (EOS) assessments should be performed Performed 28 days after last dose of study intervention

Optional, should be obtained for participants taking part in the skin biopsy subgroup or the photograph subgroup. Consent can be obtained up to Visit 3.

In exceptional cases, e.g., if test results are not available in time, SARS-CoV-2 test (PCR test or similar test) may be performed locally.

First dose of study intervention should only be taken after all baseline assessments are completed. Daily assessment should start 7 days before randomization visit.

At select study sites (optional): Photographs of a representative area of AD involvement (e.g., the lesioned area used for EASI assessments). Instructions for taking the photographs will be provided in a photography manual.

Only (S)AEs which are related to protocol-required study procedures should be recorded before start of study intervention (all other events should be recorded as medical history).

- Safety panel (central lab) will include parameters listed in Appendix 10.2 (Table 10-1)
- Only CRP, blood count, and urinalysis must be re-assessed at Visit 2 to rule out asymptomatic infections; further lab values only in case results from screening lab (Visit 1) require re-testing for eligibility or clinically indicated control-analyses.
- May be performed + 3 days of visit. All ECG reports are to be assessed for clinical significance by a physician.
- Blood samples (plasma and whole blood) for molecular biomarkers (optional analysis) In total 2, BM samples will be collected: 1x biomarker blood plasma and 1x biomarker whole blood. See Table 8–1 for further details to BM samples.

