Embryotoxicity and teratogenicity	BAY 1834845 was embryotoxic and, at the highest tested dose, also teratogenic in the studies on embryofetal development in mice with safety margins of less than 1 when looking at total exposure. With regard to unbound exposure, the safety margin for teratogenicity was 10 to 14.	 Exclusion of pregnant women Appropriate contraception measures for women of child-bearing potential (WOCBP) and study participants with WOCBP as partners are required. Serum pregnancy test will be performed for WOCBP at screening Visit 1 and Visit 2 and at end of study visit (EOS, 28 days after the last drug dose intake). In addition, regular urine pregnancy tests will be carried out at randomization (Visit 3) and at Visit 4

Table 2–1: Risk overview

Potential risk of clinical significance	Summary of data / rationale for risk	Mitigation strategy
		(Day 14), Visit 5 (Day 28), Visit 6 (Day 56) including the end-of-treatment visit (Day 84).
Rhabdomyolysis	In an ongoing clinical study in which a research molecule of the same drug class as BAY 1834845 was tested, a case of severe muscle damage (rhabdomyolysis) with lethal outcome was observed in a patient with a malignant disease.	 Although this case refers to a different molecule and the relationship to the study drug is yet under investigation, some measures to identify any myopathies are implemented in this study: Frequent testing of CK in serum Discontinuation in case of elevated CK or suspicion of myopathy/rhabdomyolysis Instruction of participants to abstain from intensive exercise and to report symptoms of myopathy (e.g., muscle weakness, muscle pain), change of color of urine or urinary retention Guidance for management of muscle symptoms and CK increase Unexplained cases of rhabdomyolysis defined as AESI.
	Study procedures	
Blood sampling (by single vein puncture and/or indwelling cannula) may be accompanied by mild pain, hematoma and in rare cases inflammation of the vessel wall or injury of a nerve.	This presents minimal risk as related documented AEs observed in prior studies are mild and were completely resolved.	All study assessments will be carried out by trained clinical staff.

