- 6. Body mass index (BMI) within the range of 18.5 to 35.0 kg/m² (inclusive) at screening (Visit 1) and randomization visits.
- 7. Women of childbearing potential (WOCBP; for definition, see Section 10.4) and male subjects able to father children must agree to use adequate contraception when sexually active. This applies since the signing of the informed consent form until 30 days after the last study intervention administration. Contraceptive use by men or women should be consistent with local regulations regarding the methods of contraception for those participating in clinical studies.

Male Participants:

Male participants are eligible to participate if they agree to the following during the study intervention period and for at least 30 days after the last dose of study intervention:

- Must agree to use contraception / barrier as detailed below:
 - Agree to use a male condom with female partner use of an additional highly effective contraceptive method with a failure rate of < 1% per year as described in Appendix 4 Contraceptive and Barrier Requirements (see Section 10.4).

or

- Be abstinent from heterosexual intercourse as their preferred and usual lifestyle (abstinent on a long term and persistent basis) and agree to remain abstinent.
- Refrain from donating sperm.

Female Participants:

- A female participant is eligible to participate if she is not pregnant or breastfeeding, and one of the following conditions applies:
 - Is a woman of nonchildbearing potential (WONCBP) as defined in Appendix 4 (see Section 10.4). Contraception and Barrier Guidance.
 - Is a WOCBP and using a contraceptive method that is highly effective (with a failure rate of < 1% per year), preferably with low user dependency, as described in Appendix 4 (see Section 10.4). Contraception and Barrier Guidance during the study intervention period and for at least 30 days after the last dose of study intervention. The investigator should evaluate the potential for contraceptive method failure (e.g., noncompliance, recently initiated) in relationship to the first dose of study intervention.
- A WOCBP must have a negative highly sensitive pregnancy test (urine) as required by local regulations within 24 hours before the first dose of study intervention, see Section 8.3.5 Pregnancy Testing.

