- Sponsor request (after discussion with the investigator), for reasons such as a significant protocol deviation or participant non-compliance.
- Study as whole is terminated by the sponsor.
- Liver safety-related discontinuation criteria are met as described in Section 7.1.1.
- Confirmed creatine kinase (CK) > 10 x ULN or clinical signs of rhabdomyolysis (Section 10.2.1).
- Herpes zoster

A participant should also be permanently discontinued from study intervention for the following **laboratory abnormalities**:

- WBC count < 1000 cells/ μ L; < 1.0 x 10⁹/L
- Absolute neutrophil count < 500 cells/ μ L; $< 0.5 \times 10^9$ /L
- Lymphocyte count < 200 cells/ μ L; < 0.2 x 10⁹/L
- Hemoglobin < 8 g/dL.

Handling of discontinuation of study intervention

For participants who permanently discontinue the study intervention, an EOT visit with all assessments as specified in the SoA (see Section 1.3) should be performed as soon as the study intervention has been discontinued. If the decision to stop the study intervention early is

taken during a site visit, this visit becomes the EOT visit. The FU visit should be performed as planned after the last dose.

After the early EOT visit, treatment with SoC may be started at the discretion of the investigator and entered into the eCRF. For zabedosertib, a wash-out period of 7 days (approximately 5 half-lives) is recommended, because there is no experience or data with a combination of zabedosertib and systemic AD treatment.

See the SoA (Section 1.3) for data to be collected at the EOT and FU and for any further evaluations that need to be completed.

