• Sexual abstinence Sexual abstinence is considered a highly effective method only if defined as refraining from heterosexual intercourse during the entire period of risk associated with the study intervention. The reliability of sexual abstinence needs to be evaluated in relation to the duration of the study and the preferred and usual lifestyle of the participant.
a) Contraceptive use by men or women should be consistent with local regulations regarding the use of contraceptive methods for those participating in clinical studies.
b) Failure rate of < 1% per year when used consistently and correctly. Typical use failure rates differ from those when used consistently and correctly.
c) Male condoms must be used in addition to hormonal contraception. If locally required, in accordance with Clinical Trial Facilitation Group (CTFG) guidelines, acceptable contraceptive methods are limited to those which inhibit ovulation as the primary mode of action.
Note: Periodic abstinence (calendar, symptothermal, postovulation methods), withdrawal (coitus interruptus), spermicides only, and lactational amenorrhea method (LAM) are not acceptable methods of contraception for this study. Male condom and female condom should not be used together (due to risk of failure from

friction).

Collection of pregnancy information:

Male participants with partners who become pregnant

- The investigator will attempt to collect pregnancy information on any male participant's female partner who becomes pregnant while the male participant is in this study. This applies only to male participants who receive study intervention.
- After obtaining the necessary signed informed consent from the pregnant female partner directly, the investigator will record pregnancy information on the appropriate form and submit it to the sponsor within 24 hours of learning of the partner's pregnancy. The female partner will also be followed to determine the outcome of the pregnancy. Information on the status of the mother and child will be forwarded to the sponsor. Generally, the follow-up will be no longer than 6 to 8 weeks following the estimated delivery date. Any termination of the pregnancy will be reported regardless of fetal status (presence or absence of anomalies) or indication for the procedure.

Female participants who become pregnant

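### Three sections give different end points for contraception and pregnancy collection; the gap matters for participants who leave without a follow-up visit and for partners of male participants

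*Protocol*

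**What the plan says.** **Contraception period.** Inclusion criterion 7 (Protocol 5.1) says of contraception: "This applies since the signing of the informed consent form until 30 days after the last study intervention administration". The sex-specific criteria repeat the period: "for at least 30 days after the last dose of study intervention".

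**Collection window.** Section 8.4.5 collects details of pregnancies in female participants and in partners of male participants from the start of treatment "until last safety FU visit, but at least until 2 weeks after the last dose of study intervention in case of early termination".

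**Appendix 4 (Section 10.4).** This covers a partner "who becomes pregnant while the male participant is in this study" and, in similar terms, a female participant whose pregnancy arises while she is taking part. Reported pregnancies go to the sponsor within 24 hours of the site learning of them and are followed to outcome.

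**Follow-up visit.** The schedule of activities places Visit 8 at "Days after last dose 28", planned for Day 112 with 3 days either side. It also applies after early stopping: "Early Discontinuation: Visit 7 (EOT) and Visit 8 (EOS) assessments should be performed". Section 7.1 agrees: "The FU visit should be performed as planned after the last dose". On withdrawal from the study, Section 7.2 asks for the visit only if it can be done.

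**Testing.** Women of childbearing potential have a central serum test at Visit 8 (Section 8.3.5). No test is scheduled for partners.

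**Reason for the precaution.** Table 2-1 (Section 2.3.1) reports embryotoxicity in mice, and teratogenicity at the highest dose, "with safety margins of less than 1 when looking at total exposure". On unbound exposure the same row gives a teratogenicity margin of 10 to 14.

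**The concern.** The plan asks participants to avoid conception for 30 days after the last dose, but it does not clearly require a contraceptive failure in that period to be recorded. Section 8.4.5 sets a calendar window for collection, Appendix 4 asks whether the pregnancy arose during participation, and neither refers to the 30 days.

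Section 7.2 discontinues a withdrawing participant from the study at the time of withdrawal. Read literally, Appendix 4 could then end collection sooner than the 2-week minimum in 8.4.5.

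Once the window has closed, the only remaining route is a pregnancy-related serious adverse event that the investigator happens to learn of and judges related, and there is no duty to look for one. A pregnancy conceived close to the last dose and otherwise uneventful could then have no form, no notification and no outcome follow-up. For a compound with embryofetal findings in mice, such a pregnancy carries useful safety information.

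**Working it through.** **Inputs from the documents**
- Contraception period: 30 days after last dose (5.1).
- Follow-up visit: 28 days after last dose, window 3 days either side, so Day 25 to Day 31 (schedule of activities). Check: 84 + 28 = 112, which matches the planned study day.
- Minimum after early termination: 14 days after last dose (8.4.5).
- Wash-out: 7 days, about 5 half-lives (6.9.3 and 7.1).

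**Input not in the documents**
- Time from conception to recognition or detection: assumed 7, 14 or 21 days.

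**Formulas**
- Shortfall = max(0, 30 - day on which collection ends).
- Latest conception captured = day on which collection ends - recognition time.

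Days are counted from the last dose; negative values fall during dosing.

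| Collection ends | Shortfall against 30 days | Latest conception captured (7 / 14 / 21 days) |
|---|---|---|
| Day 28, planned visit | 30 - 28 = 2 | 21 / 14 / 7 |
| Day 25, earliest visit | 30 - 25 = 5 | 18 / 11 / 4 |
| Day 31, latest visit | 0 | 24 / 17 / 10 |
| Day 14, minimum | 30 - 14 = 16 | 7 / 0 / -7 |

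**Women who attend Visit 8.** At Day 28 all three assumptions capture every conception during dosing and through the 7-day wash-out. At Day 25 this holds for 7 and 14 days. For 21 days, capture ends at Day 4, so the last 3 days of wash-out (7 - 4) are missed.

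**Participants followed only to the minimum.** With 7 days to recognition, the wash-out is just covered. With 14 days, no conception after the last dose is captured. With 21 days, the last week of dosing is missed too.

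**Partners.** The same arithmetic applies, but without a scheduled test capture depends on a report, so the longer recognition times are the more relevant ones.

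**Would moving the calendar end to Day 30 be enough?** It would bring the shortfall to 0, but the latest conception captured would be 30 - 7 = 23, 30 - 14 = 16 or 30 - 21 = 9. To cover conceptions through Day 30, the rule has to refer to conception date.

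**The case against.** The strongest reply is that the plan protects most participants already. Much of it stands.

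- A reader might infer that collection stops at 2 weeks for everyone who terminates early. The text does not support this. Two weeks is a minimum, and the schedule and Section 7.1 keep the 28-day visit after early discontinuation. The 16-day figure applies only to people who leave without that visit.
- A reader might infer that conceptions around the end of dosing are generally missed. For women who attend Visit 8, the serum test and the arithmetic above point the other way.
- A reader might call the 30 days the protocol's risk period. The documents use it only as a contraception period, and they put wash-out at 7 days.
- A reader might infer that a pregnancy recognised late never needs notification or outcome follow-up. Appendix 4 goes by when the pregnancy arises, so one conceived during participation and recognised afterwards can fall within its terms. The fault is that 8.4.5 reads differently.
- The total-exposure margin should not be cited alone. The unbound margin was 10 to 14, and Section 8.3.5 reports no effects in rabbits and no genotoxicity.
- The consent pages are not available, so it cannot be said that participants are not told to report later pregnancies.

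These points limit who is affected. They do not make 5.1, 8.4.5 and Appendix 4 agree, and they do not help participants who leave without a follow-up visit or partners who are not tested.

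**Conclusion.** The point holds as an inconsistency with a limited practical gap. Against the 30-day contraception period, required collection falls short by 2 days at the planned follow-up visit (0 to 5 with the window) and by up to 16 days for a participant followed only to the 2-week minimum. The two groups materially affected are participants who leave without a follow-up visit and partners of male participants.

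The shortfalls in days come directly from the protocol. The statement about which conceptions are captured rests on the assumed 7 to 21 days to recognition; across that range the 14-day window reaches from Day +7 back to Day -7. Few pregnancies are expected among 72 participants. No efficacy endpoint or analysis depends on this, and the value of correcting it lies in more complete safety information at little cost.

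**What to change.** Reconcile Section 8.4.5 and Appendix 4 with the 30-day period already in Section 5.1, using one definition in both places. Collect and follow to outcome any pregnancy in a treated participant, or in the partner of a treated male participant, with an estimated conception date from first dose to the end of that period, whenever it becomes known. State that this includes early terminators and those who withdraw, subject to any consent limits on later data, and let it replace the 2-week minimum. If the participant information does not already say so, ask participants at last contact to report such pregnancies.

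The cost is wording in two sections and possibly the participant information, plus an occasional report after the last visit. No visit, test or change to the contraception requirement is needed.
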